## 9.4 Treatments

The following treatments will be used in the study:

- **Test:** Desoximetasone topical spray, 0.15% (Taro Pharmaceuticals, U.S.A., Inc.), applied twice a day for 28 days
- **Placebo:** Vehicle spray (Taro Pharmaceuticals, U.S.A., Inc.) applied twice a day for 28 days

## CONFIDENTIAL PROTOCOL

A Randomized, Double-Blind, Placebo-Controlled, Parallel-Design, Multiple-Site Clinical Study to Evaluate the Efficacy and Safety of Desoximetasone Topical Spray, 0.15% (Taro Pharmaceuticals, U.S.A., Inc.) in Patients with Mild to Moderate Plaque Psoriasis

---

### 9.4.1 Treatments Administration

An Independent Dispenser will dispense the study medication and provide instruction on the dosing technique. The patient will be told to spray and gently rub in the study drug (until it is completely absorbed into the skin) to the affected areas twice a day (morning and evening), approximately 12 hours apart, for 28 days. To ensure compliance with the dosing technique, patients will be instructed to apply the medication under the supervision of the Independent Dispenser at the time of enrollment and then twice daily until their next scheduled visit. Patients will be provided with a dosing diary in which they will be required to record dosing dates and times. These diaries should be brought to each visit in order that the study staff may check compliance. At the end of the study, the dosing diaries will be retained in the patient's file as source documentation.

Qualified study patients will be provided with one 100 ml bottle of study medication at Visit 1 along with instructions for dosing. Bottles of study drug should be weighed before dispensing and after they are returned so the weight will be recorded. At Visit 3 (Day 14 ± 2) the first bottle should be collected and new 100 ml bottle of spray should be dispensed along with dosing instructions. This bottle will be returned at Visit 4 (Day 28 ± 2). Based on a maximum of 2 x 3 ml applications/day, 2 x 100 ml bottles of spray should provide sufficient drug for the study. Bottles will be weighed at the time of dispensing and when returned to determine that amount of drug used.

The patient will be informed to avoid smoking and proximity to heat or flame while using the product owing to the flammability of the product.

Treatment compliance will be encouraged by instructing the patient on the proper dosing technique and by the use of the daily diary. Compliance will be assessed by evaluation of the diary and overall exposure to study drug will be assessed by weighing the study drug bottles before and after use (see sections 9.4.5 and 9.6.11).

### 9.4.2 Identity of Investigational Product

The following products will be used in the study:

- **Test:** Desoximetasone topical spray, 0.15% (Taro Pharmaceuticals, U.S.A., Inc.)
- **Placebo:** Vehicle spray (Taro Pharmaceuticals, U.S.A., Inc.)

Study products will be supplied as 2 x 100 ml bottles of spray.

All randomized study medication will be blinded and packaged in blinded sealed boxes. Study medication and placebo will be packaged in identical, opaque bottles to maintain the study blind. Each bottle will be identified only by a label bearing the Sponsor name, protocol number, randomization number, treatment duration and a statement that the study medication is for Investigational Use Only. The study staff will dispense the study medication bottle only to those patients identified by the Investigator. The study staff will instruct the patients on the use and return of study drug. The patient will be instructed not

## **CONFIDENTIAL PROTOCOL**

A Randomized, Double-Blind, Placebo-Controlled, Parallel-Design, Multiple-Site Clinical Study to Evaluate the Efficacy and Safety of Desoximetasone Topical Spray, 0.15% (Taro Pharmaceuticals, U.S.A., Inc.) in Patients with Mild to Moderate Plaque Psoriasis

---

to discuss the appearance of the study medication bottle with any study personnel conducting the study visits i.e., the Investigator(s) or the Study Coordinator(s).

Individual boxes containing tubes of study medication will be packaged in blocks. One block will consist of 4 patients' worth of study medication (i.e., 2 x Test: 2 Placebo). The study medication will be shipped to each Investigator's site from a centralized pharmacy. The Principal Investigator at each site is responsible for ensuring that all study medications are stored in a locked, secure location, with access limited to the Investigator and his/her designee(s). An accurate inventory of the study medication will be maintained in accordance with federal regulations. Study medication will be stored at controlled room temperature 15-30°C (59-86°F).

Once the site has been notified that they may do so, all unused study medication and empty or partially used bottles of study medication may be returned to the Sponsor or designee.

### **9.4.3 Method of Assigning Patients to Treatment Groups**

The study drug will be randomized, packaged and blinded by an independent packaging company. Randomization will be pre-planned according to a computer-generated randomization schedule. The randomization will be generated in blocks, each containing 4 patients' worth of medication (2 x Test product and 2 x Placebo). Each patient kit will contain 2 x 100 ml bottles of study medication.

The randomization number will be a unique 4 digit number.

A perforated or two-part label will be attached to the box of drug supplies for each patient. Both pieces of the label should include the following information: protocol number, randomization number, space for patient's initials, statement that the drug is for Investigational Use Only, space for dispensing date, storage information and the Sponsor's name. One part of the label shall remain attached to the box. The other part will be removed before dispensing and attached to the patient's source documents.

At the end of the study, after all the clinical data have been entered and the study database has been locked, a copy of the randomization will be sent to the statistician.

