## CONFIDENTIAL PROTOCOL

A Randomized, Double-Blind, Placebo-Controlled, Parallel-Design, Multiple-Site Clinical Study to Evaluate the Efficacy and Safety of Desoximetasone Topical Spray, 0.15% (Taro Pharmaceuticals, U.S.A., Inc.) in Patients with Mild to Moderate Plaque Psoriasis

---

Each study site will have at least one Independent Dispenser. The role of the Independent Dispenser is to dispense and collect all study medication from the patients and to ensure the study medication logs are completed. They should not be involved in collecting any efficacy data in the study thus ensuring the integrity of the study blind.

To ensure information that could potentially bias handling of data is not disclosed, the clinical packaging company will hold the randomization scheme until database lock. For each patient an individual code break card describing the actual treatment will be provided with the study medication, to be unblinded only in the case of medical emergency and should be kept at the site with the study documents when the study is completed. Whenever possible, the Novum Medical Monitor must be contacted before breaking the blind for any patient. The code break cards should be stored in a secure location at all times and maintained at the site for all randomized patients after the completion of the study.

At the conclusion of the study, after the database has been locked, each site will be sent an envelope containing the full study randomization scheme that should be retained with the study documents in case needed during an FDA Inspection.

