## **CONFIDENTIAL PROTOCOL**

A Randomized, Double-Blind, Placebo-Controlled, Parallel-Design, Multiple-Site Clinical Study to Evaluate the Efficacy and Safety of Desoximetasone Topical Spray, 0.15% (Taro Pharmaceuticals, U.S.A., Inc.) in Patients with Mild to Moderate Plaque Psoriasis

---

collection. The clinical site will make all records associated with the study available to Novum's representative during such visits and audits

The study may be subject to audit by the Sponsor, Sponsor Representative or by regulatory authorities. If such an audit occurs the Investigator must agree to allow access to required patient records. By signing this protocol, the Investigator grants permission to personnel from the Sponsor, its representatives and appropriate regulatory authorities for on-site monitoring of all appropriate study documentation, as well as on-site review of study procedures.

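### The protocol that sites hold discloses a fixed block of 4 and packages kits by block, so unblinding one patient informs on the others in that block

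*Protocol*

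**What the plan says.** Section 9.4.3 gives one block length and its content: "The randomization will be generated in blocks, each containing 4 patients", made up of "2 x Test product and 2 x Placebo". Section 9.4.2 repeats both facts and carries them into the physical supply: "Individual boxes containing tubes of study medication will be packaged in blocks". The kits then go to each site, where the Investigator and designees have access to the locked stock.

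Three other provisions matter here:

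- One part of the kit label, which bears the randomization number, reaches the patient's file (section 9.4.3): "The other part will be removed before dispensing and attached to the patient's source documents".
- Section 9.4.4 puts the means of unblinding at the site: "For each patient an individual code break card describing the actual treatment will be provided with the study medication". A break is reserved for medical emergency, with the Medical Monitor contacted first where possible.
- The Investigator signs the protocol (section 11.2.10) and scores IGA and TLSS at every clinic visit (sections 9.5.1 to 9.5.4).

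The protocol also sets safeguards. Section 9.4.2 says "Study medication and placebo will be packaged in identical, opaque bottles to maintain the study blind", inside sealed boxes. Section 9.4.4 assigns dispensing to an Independent Dispenser who takes no part in efficacy data, and leaves the scheme with the packaging company until database lock.

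**The concern.** Section 9.4.4 keeps the randomization scheme off site so that biasing information does not reach those who handle data. Sections 9.4.2 and 9.4.3 then tell the same people how the scheme is built. With a known, constant block of 2 Test and 2 Placebo, knowledge about one patient becomes partial knowledge about three others.

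Both co-primary endpoints are graded by eye on ordinal scales, and both must reach significance. Enrolment also depends on the Investigator's grading (IGA of 2 or 3, plaque elevation, choice of Target Lesion; section 9.6.12). If the arm of a block-mate becomes known or strongly suspected, both the choice of whom to enrol next and the scoring of patients already enrolled are open to influence. The protocol describes no site task that uses the block length.

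**Working it through.** **Inputs.** Block of 4, 2:2 (9.4.2, 9.4.3); up to 120 enrolled, so 120/4 = 30 blocks; planned success rates 40% Test and 12% Vehicle (10.2). Sequential use of a block at one site is an assumption; section 9.4 does not state kit order or how blocks are allocated to sites.

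**1. The plan's own figure.** Section 10.2 gives 89% power for 50 per arm. With a pooled-variance Z-test, the null standard error is √(2 × 0.26 × 0.74/50) = 0.0877 and the alternative standard error is √(0.40 × 0.60/50 + 0.12 × 0.88/50) = 0.0831. Then (0.28 − 1.96 × 0.0877)/0.0831 = 1.30, or 90.3%. Fisher's exact test gives 87.2%. The 89% is reproduced closely enough. This point does not depend on it and borrows only the two rates.

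**2. Code breaks.** Given one patient on Test, the other three places hold one Test and two Placebo. Each block-mate therefore has probability 2/3 of the opposite arm and 1/3 of the same arm; nothing is certain. Two breaks on the same arm fix the remaining two patients. Two breaks on different arms leave one of each, and nothing is certain.

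**3. All preceding assignments in the block known.** Over the 6 orderings of a 2:2 block:

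| Position | Chance it is certain | Best-guess accuracy |
|---|---|---|
| 1 | 0 | 1/2 |
| 2 | 0 | 2/3 |
| 3 | 1/3 (first two on the same arm) | 1/3 × 1 + 2/3 × 1/2 = 2/3 |
| 4 | 1 | 1 |

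Certain: (1/3 + 1)/4 = 33.3%, or 40 of 120 patients. Accuracy: (0.500 + 0.667 + 0.667 + 1)/4 = 70.8%.

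**4. Blind intact, only success or failure of preceding patients seen.**

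- After one success, P(that patient was on Test) = 0.40/0.52 = 0.769, so P(next on Test) = 0.769 × 1/3 + 0.231 × 2/3 = 0.410.
- After one failure, P(that patient was on Test) = 0.60/1.48 = 0.405, so P(next on Test) = 0.405 × 1/3 + 0.595 × 2/3 = 0.532.
- Accuracy at position 2: 0.26 × 0.590 + 0.74 × 0.532 = 0.547.
- Full enumeration gives 0.500, 0.547, 0.569 and 0.574 for positions 1 to 4, a mean of 54.7%.
- After two successes, the weights are TT 0.16/6 = 0.0267, one of each 0.048 × 4/6 = 0.0320, and PP 0.0144/6 = 0.0024. P(next on Test) = (0.0160 + 0.0024)/0.0611 = 0.301. The denominator shows that this pattern arises in only about 6% of blocks.
- After three successes, P(fourth on Test) = 0.00576/(0.00576 + 0.0192) = 0.231.

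**5. Alternatives, with all preceding assignments known.** A fixed block of 6 gives 25.0% certain and 68.3% accuracy; a block of 8 gives 20.0% and 66.6%. A simulated random mix of 4 and 6, with the order of sizes unknown to the guesser, gives about 6% certain and about 69% accuracy. Varying the block size removes most of the certainty but little of the average guessability.

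**The case against.** A reader might infer from a printed block of 4 that investigators can work out later assignments. The documents do not support that. The two products look alike, the boxes are sealed, the dispenser is kept away from efficacy data and the scheme is held elsewhere. Unless the blind has already failed, no assignment can be deduced: even three visible successes leave the fourth patient with a 23% chance of Test. The 33% and 71% presuppose that every preceding assignment is known, and nothing in the protocol suggests code breaks would be that frequent.

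Further points have weight:

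- Success is judged at Day 28, so for outcomes to influence enrolment the preceding patients must have finished before the next is enrolled. No enrolment rate is given.
- When scoring, the assessor sees the patient's own response, and a success alone already implies a 77% chance of Test (0.40/0.52). Block membership adds much less.
- Packaging in blocks does not strictly mean that boundaries are marked at the site or that kits are used in number order.
- A small block has a purpose, which is treatment balance.

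All of this stands, and it limits the size of the point. It does not give a reason for telling sites the block length, and the safeguards protect each patient's own assignment without stopping knowledge of one patient from carrying over to block-mates. The dispenser safeguard is also loosely worded: 9.4.2 has study staff dispensing, whereas 9.4.4 gives this to the Independent Dispenser.

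**Conclusion.** This is an avoidable design weakness, not a contradiction or an arithmetical error, and it should be corrected because correction is nearly free. With the blind intact the leak is small, about 5 percentage points of guessing accuracy on average. Its importance lies in what follows a breach: a single break moves three other patients from even odds to 2:1, and a second break on the same arm identifies the whole block. The figures assume that block membership can be recognised at the site, which block packaging and numbered labels make plausible but which the protocol does not state. The outcome-based figures also assume the planned 40% and 12% rates.

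**What to change.** - Delete the block length and the 2:2 composition from sections 9.4.2 and 9.4.3, and place them in a restricted randomization specification held by the packaging company. The protocol need say only that allocation is 1:1 by a computer-generated blocked schedule.
- Ship and store kits without visible block bundling.
- Optionally, for kits not yet packaged, generate the list with an undisclosed random mix of block sizes, for example 4 and 6.
- Align the wording on who dispenses in 9.4.2 with 9.4.4.

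The first two changes cost no patients, power or site staff. Mixed sizes need a new list and allow a within-block imbalance of 3 rather than 2. The text is at Revision 5, dated 02/15/17, and does not say how many kits are already packaged. Where sites hold this version, deleting the sentences cannot undo the disclosure, so the benefit there depends on changing the remaining list and the packaging.

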### **9.4.4 Study Blind**

The Investigator, staff at the study site, study monitors, and data analysis/management personnel will be blinded to the patient assignment. To maintain the Investigator-Blind, the Independent Dispenser will be responsible for dispensing and collecting study medication. The patient will be requested not to discuss the appearance of the study medication with the Investigator or study staff.

## CONFIDENTIAL PROTOCOL

A Randomized, Double-Blind, Placebo-Controlled, Parallel-Design, Multiple-Site Clinical Study to Evaluate the Efficacy and Safety of Desoximetasone Topical Spray, 0.15% (Taro Pharmaceuticals, U.S.A., Inc.) in Patients with Mild to Moderate Plaque Psoriasis

---

Each study site will have at least one Independent Dispenser. The role of the Independent Dispenser is to dispense and collect all study medication from the patients and to ensure the study medication logs are completed. They should not be involved in collecting any efficacy data in the study thus ensuring the integrity of the study blind.

To ensure information that could potentially bias handling of data is not disclosed, the clinical packaging company will hold the randomization scheme until database lock. For each patient an individual code break card describing the actual treatment will be provided with the study medication, to be unblinded only in the case of medical emergency and should be kept at the site with the study documents when the study is completed. Whenever possible, the Novum Medical Monitor must be contacted before breaking the blind for any patient. The code break cards should be stored in a secure location at all times and maintained at the site for all randomized patients after the completion of the study.

At the conclusion of the study, after the database has been locked, each site will be sent an envelope containing the full study randomization scheme that should be retained with the study documents in case needed during an FDA Inspection.

### 9.4.5 Compliance

Patients will be provided with a diary to record the time and date of dosing, other concomitant medications and adverse events. Patients taking fewer than 75% or more than 125% of the required doses, or who missed scheduled applications for > 3 consecutive days will be considered non-compliant with dosing. Compliance with dosing will be verified by the use of the patient diaries.

## 9.5 Study Conduct

### 9.5.1 Visit 1 (Day 1): Randomization

1. **Informed Consent/Accent:** Patients who are willing to comply with study procedures will read and sign the informed consent/assent. Patients under the age of majority will read and sign the assent to participate form and their parent or legal guardian must sign the consent form.
2. **Medical History:** Review the patient's demographic and medical history.
3. **Height/Weight and Vital Signs:** The patient's height (meters) and weight (kg) will be measured. The patient's vital signs will be recorded (pulse, blood pressure, temperature and respiration rate).
4. **Dermatological Assessment:** Clinical signs and symptoms of psoriasis will be evaluated by the Investigator based on the following:
  - % BSA assessment (Appendix A)

## CONFIDENTIAL PROTOCOL

A Randomized, Double-Blind, Placebo-Controlled, Parallel-Design, Multiple-Site Clinical Study to Evaluate the Efficacy and Safety of Desoximetasone Topical Spray, 0.15% (Taro Pharmaceuticals, U.S.A., Inc.) in Patients with Mild to Moderate Plaque Psoriasis

---

- IGA Score (Appendix C)
- TLSS Score (Appendix B)
- PASI Score (Appendix D)
- Application Site Reactions (Appendix E)

5. **Pregnancy Test:** A pregnancy test will be required of all female patients of childbearing potential before enrollment.
6. **Concomitant Medication:** Review the patient's use of concomitant medication within the last 12 weeks.
7. **Inclusion/Exclusion Criteria:** Confirm that the patient meets all inclusion/exclusion criteria.
8. **Dispense Study Product:** The Independent Dispenser will weigh and dispense one bottle of study drug to eligible patient with instructions. The first dose of study medication should be administered at the site, under supervision, during this visit.
9. **Provide Dosing Diary:** Provide Diary with instructions for dosing and completing the diary.
10. Schedule Visit 2.

### 9.5.2 Visit 2 (Day 7 ± 2): Interim Visit

1. **Vital Signs:** The patient's vital signs will be recorded (pulse, blood pressure, temperature and respiration rate).
2. **Dermatological Assessment:** Clinical signs and symptoms of psoriasis will be evaluated by the Investigator based on the following:
  - % BSA assessment (Appendix A)
  - IGA Score (Appendix C)
  - TLSS Score (Appendix B)
  - PASI Score (Appendix D)
  - Application Site Reactions (Appendix E)
3. **Concomitant Medication:** Review the patient's use of any new or ongoing concomitant medications since Visit 1.
4. **Adverse Events:** Review and report any AEs since Visit 1.
5. **Diary Review:** Collect and review patient's dosing diary for compliance and provide new diary.
6. Schedule Visit 3.

## **CONFIDENTIAL PROTOCOL**

A Randomized, Double-Blind, Placebo-Controlled, Parallel-Design, Multiple-Site Clinical Study to Evaluate the Efficacy and Safety of Desoximetasone Topical Spray, 0.15% (Taro Pharmaceuticals, U.S.A., Inc.) in Patients with Mild to Moderate Plaque Psoriasis

---

### **9.5.3 Visit 3 (Day 14 ± 2): Interim Visit**

1. **Vital Signs:** The patient's vital signs will be recorded (pulse, blood pressure, temperature and respiration rate).
2. **Dermatological Assessment:** Clinical signs and symptoms of psoriasis will be evaluated by the Investigator based on the following:
  - % BSA assessment (Appendix A)
  - IGA Score (Appendix C)
  - TLSS Score (Appendix B)
  - PASI Score (Appendix D)
  - Application Site Reactions (Appendix E)
3. **Concomitant Medication:** Review the patient's use of any new or ongoing concomitant medications since Visit 2.
4. **Adverse Events:** Review and report any AEs since Visit 2.
5. **Collect Study Product:** The first bottle of study product will be collected and weighed.
6. **Diary Review:** Collect and review patient's dosing diary for compliance and provide new diary.
7. **Dispense Study Product:** Independent Dispenser will weigh and dispense a new bottle of study product corresponding to the patient's randomization number.
8. Schedule Visit 4.

### **9.5.4 Visit 4 (Day 28 ± 2): End of Treatment**

1. **Vital Signs:** The patient's vital signs will be recorded (pulse, blood pressure, temperature and respiration rate).
2. **Dermatological Assessment:** Clinical signs and symptoms of psoriasis will be evaluated by the Investigator based on the following:
  - % BSA assessment (Appendix A)
  - IGA Score (Appendix C)
  - TLSS Score (Appendix B)
  - PASI Score (Appendix D)
  - Application Site Reactions (Appendix E)
3. **Pregnancy Test:** A pregnancy test will be required of all female patients of childbearing potential at the last study visit.

## CONFIDENTIAL PROTOCOL

A Randomized, Double-Blind, Placebo-Controlled, Parallel-Design, Multiple-Site Clinical Study to Evaluate the Efficacy and Safety of Desoximetasone Topical Spray, 0.15% (Taro Pharmaceuticals, U.S.A., Inc.) in Patients with Mild to Moderate Plaque Psoriasis

---

4. **Concomitant Medication:** Review the patient's use of any new or ongoing concomitant medications since Visit 3.
5. **Adverse Events:** Review and report any AEs since Visit 3.
6. **Evaluation of Patient Compliance to the Protocol:** Independent dispenser will collect and review patient's dosing diary and record total number of doses administered since Visit 3.
7. **Collect Study Product:** The second bottle of study product will be collected and weighed.
8. **Diary Review:** Collect and review patient's dosing diary for compliance.
9. **Discharge:** Review completeness of all source documents for patient and discharge from the study.

